#### **8.5.5. Primary Efficacy Analysis**

##### **8.5.5.1. Co-Primary Endpoints**

The first two primary endpoints (12 weeks and 24 weeks) will each be analyzed using an analysis of covariance model with PC\_PN0-12 and PC\_PN0-24 serving as the dependent variable for each respective analysis. Treatment group and the randomisation stratification variables will serve as factors and the baseline %PN value will serve as a covariate in each analysis. In each analysis, the higher dose group will be compared to placebo group first. The high-dose comparison will be tested at the 0.025 two-sided significance level at each timepoint. If the high-dose comparison at a particular timepoint is significant at  $p < 0.025$ , then the low-dose comparison with placebo (at the same timepoint) will be tested at the 0.025 level.

The second co-primary endpoints are responder endpoints, calculated as continuous responder comparisons at 12 weeks and again at 24 weeks. Each test will be carried out at the 1-sided  $p < 0.10$  significance level.

The trial will have shown benefit if any group comparison stated above is shown to be superior to placebo, at the same time (12 or 24 weeks, or both), each at the stated significance level.

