---	---

Study Duration	Each subject is expected to be treated in the study for 24 weeks, and to participate for up to 104 weeks including the long-term safety follow-up period: The primary portion of the study is 28 weeks: 24 weeks of treatment plus a 4 week initial safety follow-up. The total length of the study is 104 weeks: 28 weeks of the primary portion plus 76 weeks of long-term safety and follow-up evaluations.
Primary Efficacy Endpoints	
This trial has two co-primary endpoints.
 
The first co-primary endpoints are the percent changes in %PN (<math>PC\_PN_{0-t}</math>) from baseline based on caloric intake to 12 weeks and again to 24 weeks. Each endpoint is calculated as:
 $PC\_PN_{0-t} = 100 \times \frac{\%PN_{Baseline} - \%PN_t}{\%PN_{Baseline}}$ 
where:
 
<math>t = 12</math> or <math>24</math> weeks.
 
<math>\%PN</math> = % Parenteral Nutrition (feeding) calculated as parenteral calories divided by calculated total caloric requirements (the Schofield equation (1)).
 
 
• Each <math>PC\_PN_{0-t}</math> observation will be computed as an average over a single week.
 
• Thus, for example, <math>PC\_PN</math> at 12 weeks will be the average of <math>PC\_PN</math> over days 78 to 84.
 
 
<math>PC\_PN</math> at 24 weeks will be the average of <math>PC\_PN</math> over days 162 to 168.
 
The study will have shown benefit if either <math>PC\_PN_{0-12}</math> or <math>PC\_PN_{0-24}</math> in the treated group is statistically significantly superior to placebo.
 
The second co-primary endpoints are responder endpoints. The outcome variable for each subject will be the same outcome as for the first primary, but the statistical test will be calculated as continuous responder comparison at 12 weeks and again at 24 weeks.

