Statistical Analysis of Endpoints	
First Co-Primary Endpoints
 
The primary endpoints (measured at 12 weeks and 24 weeks) will each be analyzed using an analysis of covariance model with PC_PN0-12 and PC_PN0-24 serving as the dependent variable for each respective analysis. Treatment group and the randomisation stratification variables will serve as factors and the baseline %PN value will serve as a covariate in each analysis. In each analysis, the higher dose group will be compared to placebo group first. The high-dose comparison will be tested at the 0.025 two-sided significance level at each timepoint. If the high-dose comparison at a particular timepoint is significant at <math>p < 0.025</math>, then the low-dose comparison with placebo (at the same timepoint) will be tested at the 0.025 level.
 
Second Co-Primary Endpoints
 
The results will be displayed on a graph where the x-axis displays the percent reduction in %PN and the y-axis shows the proportion of infants who meet each response threshold (from 0 to 100%). The continuous responder curves for each dose vs. placebo will be compared using the Mann Whitney U test based on the 12 week data and another graph and analysis will make the similar comparison at 24 weeks. A positive outcome for the continuous responder analyses will be a one-sided p-value less than 0.10.
 
The trial will have shown benefit if any group comparison stated above is shown to be superior to placebo on both of the co-primary endpoints at the same time (12 or 24 weeks, or both), each at the stated significance level.
 
Key Secondary Endpoint
 
The key secondary endpoint will be analyzed using a stratified log-rank test with factors for treatment group and the randomization stratification variables. Separate analyses will be carried out for each dose group. Time to the endpoint will be taken as the 14th day of consecutive less than 10% PN.

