#### **Co-Primary Endpoint (responders)**

The continuous responder analysis will be displayed graphically where the  $x$ -axis displays the percent reduction in %PN and the  $y$ -axis shows the proportion of infants who meet each response threshold (from 0 to 100%). The continuous responder curves for each dose vs. placebo will be compared using the Mann Whitney U test based on the 12 week data and another graph and analysis will make the similar comparison at 24 weeks. Each test will be carried out at the 1-sided  $p < 0.10$  significance level.

The trial will have shown benefit if any group comparison stated above is shown to be superior to placebo on both of the co-primary endpoints at the same time (12 or 24 weeks, or both), each at the stated significance level.

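### The rule that decides trial success is stated in three different ways, and the version in the primary analysis section drops the requirement to win on both co-primary endpoints

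*Combined protocol and SAP*

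**What the plan says.** The success rule appears in four places.

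- **Synopsis, Statistical Analysis of Endpoints.** A dose comparison must be "shown to be superior to placebo on both of the co-primary endpoints at the same time (12 or 24 weeks, or both").
- **Section 8.1.2, Co-Primary Endpoint (responders).** The same rule: "superior to placebo on both of the co-primary endpoints at the same time (12 or 24 weeks, or both), each at the stated significance level".
- **Section 8.5.5.1, Co-Primary Endpoints.** "The trial will have shown benefit if any group comparison stated above is shown to be superior to placebo, at the same time", followed by the same bracket on 12 or 24 weeks and the same closing words on significance levels. The reference to both co-primary endpoints is absent.
- **Synopsis, Primary Efficacy Endpoints.** "The study will have shown benefit if either" the 12-week or the 24-week percent change in %PN "in the treated group is statistically significantly superior to placebo". No responder condition is attached.

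The test levels are the same throughout. For the means, "The high-dose comparison will be tested at the 0.025 two-sided significance level at each timepoint", and the low dose is tested at a time point only after the high dose has won there. For the responder curves, "A positive outcome for the continuous responder analyses will be a one-sided p-value less than 0.10". No multiplicity correction or dose order is given for the responder tests.

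Section 8.1 makes the SAP prevail over the protocol. Section 8.1.2 promises SAP methods that protect the Type I error rate over the primary and key secondary endpoints. The supplied document contains no SAP text that states the success rule.

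**The concern.** These sentences decide whether the trial is positive, and they can give opposite verdicts on the same data.

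- Suppose the best results are an ANCOVA p of 0.10 and a one-sided Mann-Whitney p of 0.08. The trial fails under 8.1.2. Under the literal wording of 8.5.5.1 it could be called positive, because the responder test is one of the comparisons listed just above the rule and has met its own level.
- Suppose the high-dose ANCOVA gives p = 0.02 and the one-sided Mann-Whitney p is 0.12. The synopsis endpoint row declares benefit. Under 8.1.2 that comparison fails.

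The first conflict bears on the false-positive rate. The stated 0.05 control in 8.1.2 covers the mean endpoint only, so it does not limit a claim resting on the responder tests. The second conflict leaves the error rate nearly unchanged, but the verdict would depend on which page is read. If the conflict is still there at unblinding, choosing a reading becomes a post hoc choice of result.

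**Working it through.** **Inputs from the protocol.** Means: two-sided 0.025 at each of two time points, high dose before low dose. Responders: one-sided 0.10 per test, two doses by two time points. Allocation 1:1:1; 45 per arm, difference 12 points (42 against 30), SD 20 (section 8.4).

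**Assumed, because the documents do not give them.** The correlation between the 12- and 24-week outcomes (ρ); the share of outcome variance explained by the ANCOVA covariate (R²); the low-dose effect; normal outcomes unless stated. The correlation between the two dose comparisons is 0.5, because they share the placebo arm.

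**Step 1: the plan's own figure.** Bonferroni over the two time points gives 0.025 + 0.025 = 0.05, as 8.1.2 states for the means. In the favourable direction the limit is 0.0125 + 0.0125 = 0.025. Under the both-endpoints rule every success requires a significant high-dose ANCOVA at Week 12 or Week 24, so 0.025 also caps the false-claim rate of that rule.

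**Step 2: 8.5.5.1 read literally.** With independent tests, four responder tests give 1 − 0.9⁴ = 0.344 and two give 1 − 0.9² = 0.19. Correlation lowers this. Simulated z-statistics under the global null (2,000,000 draws; critical values 1.2816 for responders and 2.2414 for means) give:

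| Event under the null | ρ = 0.3 | 0.5 | 0.7 | 0.9 |
|---|---|---|---|---|
| Any of four responder tests positive | 0.288 | 0.271 | 0.249 | 0.215 |
| Either high-dose responder test positive | 0.178 | 0.168 | 0.154 | 0.131 |
| High-dose mean test positive at either time (cap for the 8.1.2 rule) | 0.024 | 0.024 | 0.021 | 0.018 |
| Literal 8.5.5.1 positive, mean test negative | 0.263 | 0.247 | 0.227 | 0.197 |

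The second row is shown because 8.5.5.1 names no dose for the responder tests.

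A separate simulation with actual t-tests and Mann-Whitney tests (20,000 trials per setting, 45 per arm, ρ from 0.9 to 0) agrees: 22% to 31% for the literal rule, 1.7% to 2.6% for the both-endpoints rule.

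**Step 3: mean-only rule against both-endpoints rule.** Without covariates and with normal data, every significant mean result also passed the Mann-Whitney test at 0.10. The two can part because the ANCOVA is covariate-adjusted and the Mann-Whitney test is not. In simulated trials with one ANCOVA covariate:

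- Null, R² 0 or 0.4, ρ 0.5 or 0.9: the rules disagree in at most about 0.4% of trials.
- Planned effect in both doses, 45 per arm, ρ = 0.7:

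| | R² = 0 | 0.2 | 0.4 | 0.6 |
|---|---|---|---|---|
| High-dose ANCOVA wins that fail Mann-Whitney | 0% | 1.1% | 3.3% | 6.0% |
| Chance of success, mean-only rule | 0.825 | 0.905 | 0.976 | 0.999 |
| Chance of success, both-endpoints rule | 0.825 | 0.903 | 0.973 | 0.995 |

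- Planned effect in the high dose only: the chance of success drops by 0.005, 0.019 and 0.029 at R² 0.2, 0.4 and 0.6 (ρ = 0.7), and by 0.046 at R² 0.6 with ρ = 0.9.

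**Step 4: a non-normal case.** Assume 30% of high-dose infants and 10% of placebo infants reach 100% reduction, the rest being alike, with 45 per arm and a single comparison. The chance of success is 51% on the mean alone, 48% on both endpoints and 67% on either.

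**The case against.** The strongest reply is that 8.5.5.1 contains an obvious slip. It still speaks of one time point and of each result meeting its level, words that have little purpose if one test is enough. The full rule stands twice elsewhere, including in the section devoted to these tests. The commitment in 8.1.2 to protect the Type I error rate cannot be squared with a false-claim rate above 20%. The SAP prevails and is to be signed before data lock, so it may already settle the matter. The synopsis sentence on the mean endpoint comes before the responder endpoint is introduced and can be read as the 12-or-24-week rule for that endpoint alone.

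Much of this stands. The intended rule is very likely the both-endpoints rule, and 21-29% is the cost of a literal reading, not a forecast. The figures in steps 3 and 4 depend on the shape of the outcome distribution, and the simulated ANCOVA used one covariate without the stratification factors. The added gating sentence proposed below largely spells out what 8.1.2 already implies.

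What does not stand is that nothing needs changing. The defective sentence sits in the primary analysis section, from which an SAP author would naturally work. The synopsis endpoint row speaks of the study showing benefit, which is a trial-level claim. No supplied text says which version governs.

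**Conclusion.** The concern holds. Three different success rules are in force in the current text. Read literally, 8.5.5.1 raises the chance of a false claim under the global null to about 21-29% (13-18% if only the high-dose responder tests count), against about 1.8-2.4% in the favourable direction under the rule in 8.1.2. The two readings disagree in about 20-26% of null trials. These ranges rest on an assumed 12/24-week correlation of 0.9 to 0.3, and the conclusion is the same across that range.

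The mean-only sentence in the synopsis matters less. It disagrees with 8.1.2 in at most about 0.4% of null trials. At the planned effect it disagrees in 0-0.5% of trials if both doses work equally, and in 0.5-4.6% if the low dose has no effect and R² is 0.2 to 0.6. Because this is the rule that decides the trial, it must be corrected before unblinding.

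**What to change.** 1. In 8.5.5.1, restore the missing condition so that the sentence matches 8.1.2: "superior to placebo on both of the co-primary endpoints at the same time (12 or 24 weeks, or both), each at the stated significance level".
2. In the synopsis row on primary efficacy endpoints, replace the either-time-point sentence with the same rule.
3. Add one sentence: a responder result for a given dose and time point counts only if the ANCOVA for that dose and time point is significant under the step-down.
4. Carry the identical text into the SAP, since the SAP prevails.

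This replaces two sentences and adds one. Relative to the 8.1.2 rule there is no cost. Relative to a mean-only rule, the chance of trial success at 45 per arm falls by at most 0.5 points if both doses work equally, and by up to 4.6 points in the least favourable setting examined with normal outcomes (no low-dose effect, R² 0.6, ρ 0.9). With 40 per arm, 0%, 1.1%, 4.0% and 7.8% of significant high-dose ANCOVAs fail the Mann-Whitney test at R² 0, 0.2, 0.4 and 0.6. If the sponsor in fact intends a mean-only rule, the plan should say so in all four places and stop calling the responder analysis co-primary.

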#### **8.5.5.2. Key Secondary Endpoint**

The key secondary endpoint will be analyzed using a stratified log-rank test with factors for treatment group and the randomization stratification variables.

#### **8.5.5.3. Other Secondary Endpoints**

The SAP will describe the analyses planned for the other secondary endpoints.

#### **8.5.6. Sensitivity Analyses**

The SAP will describe the sensitivity analyses planned for the primary and key secondary endpoints.

#### **8.5.7. Treatment of Missing Values**

The SAP will describe the planned approaches for missing primary and key secondary endpoints.

#### **8.5.8. Analyses of Follow-up Data**

In this 24-week study, primary efficacy is measured at 12 and 24 weeks. Data lock will occur after all subjects have completed 24 weeks in the trial, before which the SAP will have been finalized and signed. The final statistical report will include outcomes up to and including 24 weeks.

#### **8.5.9. Interim Analysis**

As described in Section 8.1.1, a blind review of the data will be performed during the study in order to estimate the variance.

A Data Safety Monitoring Board (Section 10.3) will review the ongoing data to ensure safety of the subjects.

No formal interim analysis of efficacy will be performed.

### **9. DATA COLLECTION, STUDY MONITORING, AND DATA DISCLOSURE**

#### **9.1. DATA COLLECTION AND REPORTING**

The Investigator will maintain adequate and accurate source documents designed to record all observations and other pertinent data for each subject treated with the study drug.

Study personnel at each site will enter data from source documents corresponding to a subject's visit into the protocol-specific electronic Case Report Form (i.e., Electronic Data Capture (EDC) system) when the information corresponding to that visit is available. Subjects will not be identified by name in the study database or on any study documents to be collected by the Sponsor (or designee), but will be identified by a site number, subject number and initials. An electronic CRF will be completed for each subject who is assigned a study number and for whom a study-approved ICF is signed and dated. For all entries into the EDC that are not source electronic data, the data entries must be supported by original source documentation (e.g., laboratory reports, medical records) maintained at the investigational site. If a correction is required for an EDC, the time and date stamps track the person entering or updating EDC data and create an electronic audit trail.

The Investigator will make safety assessments (AEs, vital signs, results from physical examinations, and laboratory tests) on an ongoing basis. The Investigator is responsible for all information collected on subjects enrolled in this study. All data collected during the course of this study must be reviewed and verified for completeness and accuracy by the Investigator.

If a subject is lost to follow-up, (i.e., fails to return for scheduled visits) every reasonable effort must be made to contact the subject's parent or guardian in order to determine why the subject failed to return. All actions taken in this regard will be documented and dated in the CRF.

The investigator is required to electronically sign the EDC at appropriate times. The investigator's signature on the CRF serves to certify that the data collected for each subject is accurate, complete and legible. A copy of the CRF will remain at the study site at the completion of the study.

All procedures for the handling and analysis of data will be conducted using good computing practices meeting FDA guidelines for the handling and analysis of data for clinical trials.

## **9.2. STUDY MONITORING**

The Sponsor's designees will monitor all aspects of the study carefully with respect to cGCPs and SOPs for compliance with applicable government regulations. The investigator is responsible for providing all study records, including eCRFs, source documents, medical history, etc., for review and inspection by the clinical monitor.

EDC (CRFs) will be periodically monitored and source verified against corresponding source documentation (e.g., office and clinical laboratory records) for each subject. Clinical monitors will evaluate periodically the progress of the study, including the verification of appropriate consent form procedures, review of drug accountability and study drug preparation procedures, adherence to dosing procedures, the investigator's adherence to the protocol, maintenance of records and reports, review of source documents for accuracy, completeness, and legibility, and review of study regulatory documents, including, but not limited to: study agreement, study insurance, study approval letters by the IRB/IEC and the Regulatory Authority, site staff CV and

financial statements, study forms, protocol signature page, etc. In addition, the monitor shall review completed electronic case report form (eCRF) and study documentation for accuracy and completeness, and protocol compliance. The monitor should assure that data captured in the eCRF is fully supported by the source documents. Clinical monitors will also ensure that all protocol requirements, applicable Food and Drug Administration (FDA) regulations (CFR Title 21 Parts 50, 56, and 312 and ICH Guidelines for GCP - E6), other requirements, and Investigator's obligations are being fulfilled.

By signing this protocol, the Investigator grants permission to the Sponsor (or designee), and appropriate regulatory authorities to conduct on-site monitoring and/or auditing of all appropriate study documentation.

Apart from assuming responsibility for the communication between the investigator and the Sponsor, the clinical monitor duties include:

- On-site visits; and
- Review of study documents and results.

On-site monitoring visits include pre-study/qualification visits, initiation visits, interim monitoring visits and, a close-out visit at the end of the study. At the close of the study, the monitor will be required to make a final on-site visit to assure that all study data has been properly completed.

Reports of on-site visits shall be made by the monitor and should include, as applicable, resolution of concerns and queries, completion of appropriate follow-up activities, completion of assigned tasks, and corrective actions. Monitoring visits Follow-up letters will be sent to the site for filing and adherence.

All data generated in the current clinical investigation will be managed according to relevant guidelines (e.g., GCP, 21 CFR Part 11).

### **9.3. CONFIDENTIALITY, DATA DISCLOSURE, AND PUBLICATION**

Subject medical information obtained as a result of this study is considered confidential. Disclosure to third parties other than those noted below is prohibited. All reports and communications relating to subjects and their parent(s) or guardians(s) in this study will identify all persons only by their initials and number. Medical information resulting from a subject's participation in this study may be given to the subject's personal physician or to the appropriate medical personnel responsible for the subject's welfare. Data generated as a result of this study are to be available for inspection on request by FDA or other government regulatory agency auditors, the Sponsor, the Sponsor-assigned clinical monitor (or designee), and the IRB/IEC.

All laboratory specimens, evaluation forms, reports, and other records that leave the site will be identified by a coded number to maintain subject confidentiality. All records will be maintained in lockable file cabinets. All computer entry and networking programs will be identifiable only by coded numbers. Clinical information will not be released without written permission from the subject's parent or guardian, except as necessary for monitoring by the IRB, the FDA, or representatives of the study Sponsor.

Any information, inventions, or discoveries (whether patentable or not), innovations, suggestions, ideas, and reports, made or developed by an investigator as a result of conducting this study shall be promptly disclosed to the Sponsor and shall be the sole property of the Sponsor. The Investigator agrees, upon the Sponsor's request and at the Sponsor's expense, to execute such documents and to take such other actions, as the Sponsor deems necessary or appropriate, to obtain patents in the Sponsor's name covering any of the foregoing.

The results of this study will be published under the direction of the Sponsor. Results will not be published without prior review and approval by the Sponsor.

## **10. PROTECTION OF HUMAN SUBJECTS**

### **10.1. DECLARATION OF HELSINKI**

Both the Investigator and the Sponsor will ensure that the study is conducted in agreement with the Declaration of Helsinki, ICH-GCP, and the local laws and regulation.

To maintain confidentiality, all laboratory specimens, evaluation forms, reports and other records will be identified by a coded number and initials only. All study records will be kept in a locked file cabinet and code sheets linking a subject's name to a subject identification number will be stored separately in another locked file cabinet. The Investigator must also comply with all applicable privacy regulations (e.g., Health Insurance Portability and Accountability Act of 1996).

